**Comparing Effectiveness of CSE Versus DPE for Labor Analgesia**

NCT05068661

3/22/2024

After obtaining written informed consent, parturients are randomised in a 1:1 ratio by computer-generated random sequence to CSE or DPE arms, stratified by parity (nulliparous versus multiparous) and class of obesity (BMI <40 vs. 40-50 kg.m^-2). Allocation is concealed in sequentially numbered opaque envelopes. Patients, obstetricians, nurses, and anesthesia providers involved in follow-up of labour analgesia and data collection are blinded to group allocation. The anesthesia provider placing the neuraxial block and the supervising attending anesthesiologist are not involved in data collection or in follow up of labour analgesia.

Before neuraxial placement, all patients have an intravenous catheter placed with automated non-invasive blood pressure, pulse oximetry, and external tocodynamometry monitors applied. All women receive a 500 ml intravenous bolus of crystalloid solution immediately before the initiation of neuraxial analgesia. The epidural space is identified using a 17-gauge Tuohy needle with the patients in the seated position at the estimated L3-4 or L4-5 interspace, via a midline approach using a loss of resistance to saline technique. After identification of the epidural space, a needle-through-needle technique is performed using a 25-G Whitacre needle, placed into the shaft of the previously sited epidural needle to create a single dural puncture. After confirmation of free flow of CSF, initial dosing consists of intrathecal 0.25% bupivacaine 2 mg (0.8 ml) and 10 µg (0.2 ml) fentanyl in the CSE group. Subsequently, the spinal needle is removed and the epidural catheter (19-gauge Duraflex wire-reinforced multiport catheter (Smith Medical, USA)) is advanced 5 cm into the epidural space and secured with the patient in the sitting upright position, using Tegaderm clear occlusive dressing (3M, USA). In the DPE group, after confirmation of free flow of CSF, the spinal needle is withdrawn and the epidural catheter advanced 5 cm into the epidural space. After negative aspiration for blood and CSF, initial dosing consists of 20 ml of 0.1% ropivacaine plus fentanyl 2 µg.ml (premixed) administered in divided doses of 5 ml every 2 min. In both groups, analgesia is maintained using programmed intermittent epidural boluses of 8 ml of ropivacaine 0.1% with fentanyl 2 µg.ml every 45 min starting 30 min after the initial spinal or epidural loading dose, with patient-controlled epidural analgesia (PCEA) of 10 ml, a lockout of 10 min and maximum dose of 50 ml per hour.

If analgesia is inadequate (defined as a patient request for supplemental analgesia beyond self-administered PCEA boluses), an anesthesia provider blinded to group assignment assesses and, if warranted, administers top-up doses according to a predefined algorithm.

The end time of administration of the loading dose (end of spinal dose injection in the CSE group or epidural medication administration in the DPE group) is designated time 0 ( $t = 0$ ). A blinded investigator collects data at 15 and 30 min and subsequently at 2-h intervals from time zero until delivery. Analgesia is evaluated at all time points using the verbal numeric pain rating scale (NPRS) for the last contraction (0=no pain, 10=worst possible pain). The upper and lower sensory levels are evaluated at 15 and 30 min using temperature discrimination to ice. Motor blockade is assessed at all time points using the modified Bromage score.

The following additional data are recorded every 2 h until delivery: presence of pruritus; nausea; hypotension (defined as systolic blood pressure  $\leq 20\%$  from the patient's admission blood pressure); need for physician top-up; catheter adjustment and catheter replacement. We also assess for the presence of asymmetric blockade, defined as a difference  $> 2$  dermatomal sensory levels between the left and right side as assessed at 15 and 30 min or at any time that sensory levels are checked because of complaints of pain. An obstetrician blinded to group assignments accesses the electronic medical record to review tocometry and continuous fetal monitoring strips and extract uterine contraction and fetal heart rate monitoring patterns in 10-min epochs, for 1 h before and 1 h after the initial spinal (CSE group) or epidural (DPE group) dosing. On the first postpartum day, we assessed for postdural puncture headache and satisfaction with labour analgesia (0-10, 0= very dissatisfied, 10=very satisfied)

The primary outcome of the study is the quality of labour analgesia, which is defined by a composite of five components: asymmetric block after 30 min of initiation (difference in sensory level of more than two dermatomes); epidural top-up interventions; catheter adjustment; catheter replacement; failed conversion to neuraxial anesthesia for cesarean delivery, requiring general anesthesia or replacement of the neuraxial block.

Secondary outcomes include: pain scores; Bromage scores; sensory levels at 15 and 30 min; adverse events (hypotension, nausea, pruritus, postdural puncture headache, fetal heart rate changes); duration of second stage of labor; mode of delivery; total anesthetic dose; PCEA use; and overall satisfaction with analgesia.

Based on the study by Chau et al a sample size of 50 patients per group had an 80% power at alpha 0.05 to detect a reduction in the composite primary outcome from 50% in the CSE group to 22.5 % in the DPE group. To account for dropouts, we aim to enrol up to 60 patients per group to have complete data on 100 subjects.

Descriptive statistics for patient characteristics and outcomes are calculated and reported as median (IQR [range]) or number (proportion) as appropriate. The primary composite outcome is compared between exposure groups using a chi-squared test and an effect size is reported as a risk ratio. Secondary outcomes are assessed using chi-squared or Fisher exact tests as appropriate, with associated risk ratios for categorical measures and univariate log-linear regression with mean ratios for continuous measures. All p values for the secondary outcomes are adjusted for multiple comparisons using the Bonferroni-Holm method to control family-wise error rate and adjusted p values are reported. Only p values and adjusted p values < 0.05 are considered statistically significant. Analysis is performed using R version 4.3.1, with the power calculation performed using NQuery.

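### No pain score is planned before the block and the secondary model takes no covariates, so the 15- and 30-min pain comparisons are valid but give up some precision

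*Combined protocol and SAP*

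**What the plan says.** All references are to the combined protocol and SAP, which has no numbered sections.

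- **Time origin.** In the data-collection paragraph, time 0 falls after dosing in both arms. The rule begins "The end time of administration of the loading dose (end of spinal dose injection in the CSE group or epidural medication administration in the DPE".
- **Schedule.** "A blinded investigator collects data at 15 and 30 min and subsequently at 2-h intervals from time zero until delivery".
- **Pain measure.** "Analgesia is evaluated at all time points using the verbal numeric pain rating scale (NPRS) for the last contraction", on a 0–10 scale.
- **Before the block.** The placement paragraph opens with "Before neuraxial placement, all patients have an intravenous catheter placed with automated non-invasive blood pressure, pulse oximetry, and external tocodynamometry monitors applied" and goes on to a fluid bolus. It mentions no pain score. Pre-dose information is used for other outcomes: hypotension is judged against admission blood pressure, and contraction and fetal heart rate patterns are extracted "for 1 h before and 1 h after the initial spinal (CSE group) or epidural (DPE group) dosing".
- **Status of pain.** It is a secondary outcome: "Secondary outcomes include: pain scores; Bromage scores; sensory levels at 15 and 30 min".
- **Analysis.** Continuous secondary outcomes get "univariate log-linear regression with mean ratios for continuous measures", with Bonferroni-Holm adjustment across the secondary outcomes.
- **Stratification.** Randomisation is "stratified by parity (nulliparous versus multiparous) and class of obesity". Pain is not a factor.

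**The concern.** Women may ask for analgesia at different points in labour, so pain just before the block may vary between them. If that pain predicts pain 15 or 30 min later, part of the spread in the early scores is explainable, and a model that includes the baseline score removes it from the error term. The plan leaves that spread in, both because no pre-block score is scheduled and because the model has no place for one.

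At stake is the width of the intervals, and the power, for the early pain comparisons. These are small comparisons, with 50 women per arm planned for analysis, and their p values are further adjusted for multiplicity. The primary composite, its chi-squared test and the sample size are not affected.

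**Working it through.** **Plan's own figure.** There is none for pain. The only power statement concerns the primary composite, and from it I take only the 50 per arm.

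**Is any scheduled score pre-block?** The times are 15 min, 30 min and every 2 h, all counted from the end of the loading dose. Every one falls after dosing.

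**Would the model use a baseline score?** No. A univariate model contains the treatment arm alone. I assume that NPRS is among the continuous measures, as the plan does not classify it.

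**Size of the loss (illustration).**

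Inputs:
- n = 50 per arm and alpha = 0.05, from the sample-size paragraph; two-sided testing is assumed.
- Difference d = 0.5 SD: assumed.
- Correlation r between pre-block and early NPRS, 0.2 to 0.5: assumed.
- Holm family of 13: my count of the listed secondary outcomes, with the five adverse events counted singly (3 + 5 + 5 = 13). The plan does not enumerate the family. The first step is 0.05/13 = 0.0038.

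Formulas, for a linear model with one baseline covariate:
- Variance factor = 1 − r².
- Effective standardised difference = d / √(1 − r²).
- Equivalent unadjusted sample size = n / (1 − r²).
- Power from the two-sample t test, with noncentrality = effective difference × √(n/2) = effective difference × 5.

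| | no covariate | r = 0.2 | r = 0.5 |
|---|---|---|---|
| Variance factor | 1 | 1 − 0.04 = 0.96 | 1 − 0.25 = 0.75 |
| Effective difference | 0.500 | 0.5/√0.96 = 0.510 | 0.5/√0.75 = 0.577 |
| Noncentrality | 2.50 | 2.55 | 2.89 |
| Equivalent n per arm | 50 | 50/0.96 = 52.1 | 50/0.75 = 66.7 |
| Power, alpha 0.05 | 69.7% | 71.4% | 81.6% |
| Power, alpha 0.05/13 | 33% | 35% | 47% |

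The gain runs from about 2 points at r = 0.2 to about 12 points (alpha 0.05) or 14 points (first Holm step) at r = 0.5.

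**Limit of the approximation.** The plan reports mean ratios from a log-linear model, whereas these figures are for a mean difference in a linear model. They show scale and are not the power of the planned test.

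**The case against.** **There is no validity problem.** Allocation is randomised 1:1 and concealed, so the unadjusted comparison is sound. This stands in full. A reader might infer that the early pain contrast is biased, or that chance imbalance in pre-block pain is a further harm on top of lost precision. Neither follows: the unadjusted p value and interval already allow for chance imbalance. Only precision is at issue.

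**A baseline score may exist.** The schedule is the blinded investigator's follow-up list and not an inventory of all data. Parity, BMI and admission blood pressure must be recorded, yet none appears in it, and the patient characteristics to be reported are not itemised. So a reader who concludes that adjustment is impossible goes beyond the text. What the text supports is that a pre-block NPRS is not planned for. The objection does not reach the second half of the point, because the univariate model would ignore such a score anyway.

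**The gain is assumed and may be negligible.** This stands too. The documents supply neither r nor d, and at r = 0.2 the gain is under 2 points at alpha 0.05.

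**Later scores.** A reader might extend the argument to every pain time point. Nothing in the documents shows that pre-block pain predicts scores at 2 h and beyond, after programmed boluses, PCEA and possible top-ups. The point is limited to 15 and 30 min.

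**Unadjusted analysis of a secondary outcome is an acceptable choice.** True, and being listed first gives pain no formal priority. That makes this an optional improvement and not the correction of an error.

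**Conclusion.** The point holds as a modest improvement in efficiency. As written, the plan neither schedules a pre-block pain score nor uses one, so the 15- and 30-min pain comparisons, though valid, are less precise than they could be. Under the assumed correlations the saving is equivalent to having about 52 to 67 women per arm in place of 50. That rests on the assumed r, the assumed 0.5 SD difference and the linear approximation; the Holm figures also rest on a family of 13. If pre-block pain is only weakly related to early post-block pain, little would be gained.

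**What to change.** Two linked changes are needed; either alone achieves nothing for precision.

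1. Add to the data-collection paragraph one NPRS for the last contraction, recorded before needle placement, and report it by arm with the patient characteristics.
2. In the statistical analysis paragraph, replace the univariate model for the 15- and 30-min pain scores with one containing treatment arm and the pre-block NPRS. The log-linear form and mean ratio can stay. Leave the primary analysis unchanged.

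If a pre-block score is already recorded as a patient characteristic, say so; only the second change is then needed.

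**Cost.** One verbal question on a scale already in use, one data field per woman, and an amendment to a prespecified secondary model, which should be made before outcome data are examined by arm. No extra procedure or assessor is required. The benefit is limited to a secondary outcome.

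### Pruritus, nausea and hypotension have no specified assessment before 2 h, and the plan does not say what period each 2-hourly entry covers

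*Combined protocol and SAP*

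**What the plan says.** The data-collection section gives the visit schedule: "A blinded investigator collects data at 15 and 30 min and subsequently at 2-h intervals from time zero until delivery". It then assigns measurements to visits. Pain and motor block belong to every visit: "Analgesia is evaluated at all time points using the verbal numeric pain rating scale (NPRS" and "Motor blockade is assessed at all time points using the modified Bromage score". Sensory levels are taken at 15 and 30 min.

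A separate paragraph opens with "The following additional data are recorded every 2 h until delivery". Its list holds three side effects, "presence of pruritus; nausea; hypotension", and three interventions, "need for physician top-up; catheter adjustment and catheter replacement". No look-back period is stated for any of them.

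Fetal heart rate is handled differently. A blinded obstetrician is to "extract uterine contraction and fetal heart rate monitoring patterns in 10-min epochs, for 1 h before and 1 h after the initial spinal" or epidural dosing.

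The dosing section gives the two arms different loading doses by different routes. The same programmed boluses and patient-controlled settings then apply to both, "starting 30 min after the initial spinal or epidural loading dose". It also says that an automated blood pressure monitor is in place before the block, but no rule links its readings to the hypotension outcome.

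Hypotension, nausea and pruritus are named secondary outcomes. The statistical section compares categorical secondary outcomes by chi-squared or Fisher tests with risk ratios, and adjusts all secondary p values by Bonferroni-Holm.

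**The concern.** By protocol the arms differ in how analgesia is started. If the two loading doses produce different rates of itching, nausea or low blood pressure, the first half hour is a natural place to look. A blinded investigator is already collecting data then, but the plan does not ask for these three items until 120 min.

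At stake is what a finding of similar side effects would mean. The trial will test and report these outcomes. If short-lived early reactions are not captured, or are recalled up to two hours later without a time, a null comparison could reflect either similar techniques or the timing of the record, and the data would not show which.

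**Working it through.** The plan states no figure on this point, so there is none to reproduce. The check is a reading of the schedule, followed by an illustration on assumed rates.

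**Schedule**

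| Item | 15 min | 30 min | 2-hourly |
|---|---|---|---|
| Pain score, motor block | yes | yes | yes |
| Sensory levels | yes | yes | not scheduled |
| Pruritus, nausea, hypotension | not specified | not specified | yes |
| Fetal heart rate | 10-min epochs through the first hour | same | no |

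Programmed boluses start at 30 min and repeat every 45 min, so they fall at 30, 30 + 45 = 75 and 75 + 45 = 120 min. By the first scheduled side-effect entry, both arms have had two identical boluses and a third is due.

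**What an entry means.** Two readings are possible.

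- *Snapshot.* The list begins with presence of pruritus, which suggests a state at the visit. A reaction that has resolved by 120 min is then not counted.
- *Cumulative.* Top-ups, catheter adjustments and replacements in the same list are events and make sense only as occurrences since the last entry. The first entry then covers 0 to 120 min. Nothing is lost in principle, but pruritus and nausea rest on recall, and an event before 30 min cannot be told from a later one.

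**Loss of precision under the snapshot reading.** Inputs: 50 per arm (sample-size paragraph); assumed early rates of 30% v 10%; assumed fraction f of events still present at 2 h, the same in both arms. Captured rates are 0.30f and 0.10f. Power is the sum, over all pairs (a, b) of event counts, of Bin(a; 50, 0.30f) × Bin(b; 50, 0.10f) wherever the uncorrected chi-squared test rejects. The statistical section applies Holm but gives no count of comparisons; an assumed 10 gives a first step of 0.05 / 10 = 0.005.

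| f | Captured rates | Risk ratio | Power at 0.05, unadjusted | Power at 0.005 |
|---|---|---|---|---|
| 1 | 30% v 10% | 3.0 | 73% | 38% |
| 0.5 | 15% v 5% | 3.0 | 39% | 10% |
| 0.25 | 7.5% v 2.5% | 3.0 | 18% | 1% |

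In the last row the expected count is 50 × 0.05 = 2.5 per arm, so the plan's Fisher option would probably apply and the chi-squared figure is only a guide.

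The risk ratio stays at 3.0 throughout. Equal proportional loss costs precision and shrinks the risk difference (20, 10 and 5 percentage points), but does not move the planned effect measure.

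**When the risk ratio does move.** Add an assumed 10% later rate, the same in both arms and independent of early events. The recorded rate is 1 − (1 − early rate) × 0.9.

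- f = 1: (1 − 0.70 × 0.9) / (1 − 0.90 × 0.9) = 0.37 / 0.19 = 1.95
- f = 0.5: (1 − 0.85 × 0.9) / (1 − 0.95 × 0.9) = 0.235 / 0.145 = 1.62
- f = 0.25: (1 − 0.925 × 0.9) / (1 − 0.975 × 0.9) = 0.1675 / 0.1225 = 1.37

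Even with full capture, pooling early and later events takes the ratio from 3.0 to 1.95. That is the reason for a separate 30-min summary.

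**The case against.** The strongest reply is that the 2-hourly entry is cumulative, as the interventions in the same list suggest. On that reading the loading period lies inside the first entry and no event is excluded by design. This stands as a plausible reading, so the text does not support a claim that resolved reactions are certainly not counted. It does not remove the point, because no look-back is stated and recall and timing remain weak.

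A reader might also infer that the early period goes unobserved for side effects generally. The documents do not support that. Fetal heart rate changes, a listed adverse event, are extracted in 10-min epochs for an hour after dosing; motor block is scored at 15 and 30 min; and a blood pressure monitor is in place, so early readings may well exist. The gap is confined to three outcomes, and for hypotension it may be only an unspecified data source.

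Third, the documents do not say how long the effects of the two loading doses differ, and patient-controlled use and top-ups can differ between arms after 30 min. That arm differences are concentrated early is a reasonable inference from the design, but the plan does not establish it.

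Finally, the event rates are assumed, and Holm adjustment leaves limited power for these outcomes even with full capture. Both are correct, and the power figures should be read accordingly.

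**Conclusion.** The point holds for three secondary outcomes. Pruritus, nausea and hypotension have no specified entry before 120 min, although the protocol treatments differ at the loading dose and suitable visits already exist at 15 and 30 min. The meaning of each entry is also undefined. Under a snapshot reading, early events may be missed; under a cumulative reading, they rest on recall and carry no timing.

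A reader might conclude that the safety comparison is biased towards no difference. The plan does not support that as a general statement. Equal proportional loss leaves the risk ratio unchanged and costs precision. Movement towards 1 needs a further assumption, such as later events common to both arms, and resolution at different speeds in the two arms could bias the ratio either way.

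The size cannot be fixed from the documents. All power figures rest on assumed rates of 30% v 10% and assumed capture fractions; those at 0.05 ignore Holm, and those at 0.005 assume 10 comparisons. The primary composite and the sample size are unaffected. This is a cheap improvement worth making, not a threat to the trial's main conclusion.

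**What to change.** 1. Add pruritus, nausea and hypotension to the items collected at the existing 15- and 30-min visits.
2. Define every entry, at these and the 2-hourly visits, as any occurrence since the previous visit (since time 0 at the first).
3. Name the automated blood pressure readings as the source for hypotension, and say which readings count.
4. Report any event by 30 min as well as any event until delivery.

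The cost is three extra items at two visits that already take place, with no change to treatment. The 30-min summaries would add three comparisons to the Holm family, one per outcome, and so tighten the adjustment for the other secondary outcomes. Labelling them descriptive, with risk ratios and confidence intervals but no p values, avoids this. If the early items cannot be added, stating the look-back period and the blood pressure source would still resolve the ambiguity, though pruritus and nausea would continue to rest on recall.

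### The pre-dose hour of fetal heart rate and contraction data is collected, but no stated secondary analysis has a baseline term, so precision may be lost on a secondary safety outcome

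*Combined protocol and SAP*

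**What the plan says.** The combined protocol and SAP has no numbered sections. Three places bear on this point.

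- **Data collection.** A blinded obstetrician is to extract contraction and fetal heart rate patterns, in 10-minute epochs, "for 1 h before and 1 h after the initial spinal (CSE group) or epidural (DPE group) dosing". That gives six epochs before and six after dosing for each woman.
- **Secondary outcomes.** The only listed outcome that draws on these data is the last item in "adverse events (hypotension, nausea, pruritus, postdural puncture headache, fetal heart rate changes". It is not defined further. No contraction measure is listed as an outcome.
- **Statistical analysis.** "Secondary outcomes are assessed using chi-squared or Fisher exact tests as appropriate", and continuous measures get "univariate log-linear regression with mean ratios for continuous measures". No covariate is named for any outcome, and secondary p values are Holm-adjusted.

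The primary analysis is separate: "The primary composite outcome is compared between exposure groups using a chi-squared test". It does not use the monitoring data.

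**The concern.** A pre-randomised-treatment measurement of the same quantity, in the same woman, is usually the strongest available predictor of its post-treatment value. Here it is extracted by design, yet no stated test or model has a place for it. If the post-dose hour is compared alone, the between-woman variation that the pre-dose hour would explain stays in the error term. A chance difference between arms in pre-existing patterns also stays in the estimate. The comparison concerns fetal safety in about 50 women per arm and is also subject to Holm adjustment, so precision that costs almost nothing to recover is worth having.

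**Working it through.** **Inputs from the plan.** 1:1 allocation; 50 women per group with complete data; alpha 0.05 (sidedness not stated, two-sided assumed). The plan gives no SD, event rate or pre/post correlation for fetal heart rate or contractions. The correlation r and the effect size below are therefore assumptions, shown over a range.

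**The plan's own figure.** The plan states that "a sample size of 50 patients per group had an 80% power at alpha 0.05" for a fall in the "composite primary outcome from 50% in the CSE group to 22.5 % in the DPE group". The two-sided pooled chi-squared formula gives 47 per group, and power at 50 per group is 82.6%. The stated 50 is slightly conservative for that test. Nothing in it depends on the monitoring data, so this point does not touch the sample size.

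**Continuous summary of the post-dose hour.** With equal SDs before and after dosing, the variance of the arm difference relative to a post-only comparison is:

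- post-only: 1
- change score: 2(1 − r)
- baseline-adjusted (ANCOVA): 1 − r²

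The post-only standard error, in SD units, is √(2/50) = 0.20. An assumed 0.5 SD effect gives z = 0.5/0.20 = 2.50 and power Φ(2.50 − 1.96) = 70.5%. The other analyses divide 2.50 by the square root of their variance factor. At r = 0.5, for example, ANCOVA gives 2.50/√0.75 = 2.89 and power 82.3%.

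| Assumed r | ANCOVA factor | Equivalent n per arm, 50/(1 − r²) | Power, post-only | Power, change score (factor) | Power, ANCOVA |
|---|---|---|---|---|---|
| 0.3 | 0.91 | 54.9 | 70.5% | 56.1% (1.40) | 74.6% |
| 0.5 | 0.75 | 66.7 | 70.5% | 70.5% (1.00) | 82.3% |
| 0.7 | 0.51 | 98.0 | 70.5% | 89.8% (0.60) | 93.8% |

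These are normal-approximation powers at alpha 0.05 per test, before Holm. Exact t-based values are lower by less than 1 percentage point (for example 69.7% post-only, and 73.7%, 81.5% and 93.4% adjusted).

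The variance of a change score relative to ANCOVA is 2(1 − r)/(1 − r²) = 2/(1 + r), which is 1.54, 1.33 and 1.18 at the three correlations. Below r = 0.5 a change score does worse than ignoring the baseline.

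**Chance imbalance.** If 10% to 30% of women had an abnormal pre-dose pattern (assumed), the standard error of the arm difference in that proportion is √(2 × 0.10 × 0.90/50) = 6.0 points to √(2 × 0.30 × 0.70/50) = 9.2 points. Gaps of up to about 12 to 18 points lie within the 95% range (1.96 × SE).

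**Binary event.** The table does not carry over. As an illustration with assumed rates of 10% and 20%, power at 50 per arm is about 29%. Even if the 1 − r² gain is credited in full, it reaches only about 31% at r = 0.3 (n = 54.9) and 36% at r = 0.5 (n = 66.7).

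**The case against.** A reader might infer that the pre-dose hour is simply not used. The documents do not support that. The outcome is named as a change and sits among event-type adverse events, so it may well mean a new or altered pattern relative to the hour before dosing. On that reading the baseline enters through the outcome definition, and a chi-squared or Fisher test already uses it. The text neither confirms nor excludes this. A signed continuous change can be zero or negative and would not suit a log-linear mean-ratio model, which makes a categorical reading plausible.

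A reader might also infer that the comparison is biased. It is not. Under 1:1 concealed randomisation the unadjusted comparison is valid, and its type I error already allows for chance imbalance.

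Three further objections stand:

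- The power gains describe a continuous outcome that the plan does not list.
- For contractions, the gap is first a missing outcome and analysis, and only then a missing covariate.
- A covariate model could be unstable if abnormal patterns are rare.

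None of this removes the core of the point. No stated test or model has a baseline term under any reading. For a continuous summary, adjustment is (apart from one degree of freedom) at least as efficient as either a post-only or a change-score analysis. For a new-onset event, a woman's risk can still depend on her pre-dose pattern, and an unadjusted test ignores that.

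**Conclusion.** The point holds in a limited form. The pre-dose hour is collected, the stated secondary analyses contain no baseline term, and the only route by which it could enter is an outcome the plan leaves undefined. The consequence is a possible loss of precision on one secondary safety outcome. It is not bias, and it has no effect on the primary result or the sample size.

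For a continuous summary, adjustment gains about 4, 12 or 23 points of power over a post-only comparison at r = 0.3, 0.5 or 0.7, and about 19, 12 or 4 points over a change score. Both sets rest on an assumed 0.5 SD effect, equal SDs before and after dosing, 50 per arm, and two-sided alpha 0.05 before Holm. For a binary event the gain is likely to be small and cannot be sized from the documents.

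**What to change.** Before analysis, amend the statistical paragraph as follows.

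1. Define the fetal heart rate change outcome from the pre-dose and post-dose epochs, and state whether it is binary or continuous and how the pre-dose hour enters.
2. For a continuous summary, use linear regression of the post-dose-hour value on arm plus the pre-dose-hour value (ANCOVA).
3. For abnormal patterns, use a woman-level binary model with arm and the pre-dose pattern as covariate, reported as a risk ratio to match the rest of the plan. If events are sparse, use a Mantel-Haenszel risk ratio stratified by pre-dose pattern.
4. If epochs rather than women are the unit of analysis, allow for clustering within woman.
5. State whether contraction frequency is an outcome. If it is reported as one, apply the same continuous model.

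The data are already to be extracted, so no procedure, visit or sample size changes. The cost is a written outcome definition, slightly more analysis work, and the risk of an unstable model if abnormal patterns are rare, which the stratified fallback is there to cover.

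### Does the 30-minute sensory check bias the primary composite, because it reads a spinal block in the CSE arm and an epidural block in the DPE arm?

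*Combined protocol and SAP*

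**What the plan says.** The combined protocol and SAP has no numbered sections, so places are given by paragraph.

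- **Primary outcome paragraph.** The composite has five components: asymmetric block, top-up, catheter adjustment, catheter replacement, and failed conversion for cesarean delivery. The first is worded as "asymmetric block after 30 min of initiation (difference in sensory level of more than two dermatomes".
- **Outcome assessment paragraphs.** Time 0 is "The end time of administration of the loading dose". Scheduled sensory testing is limited: "The upper and lower sensory levels are evaluated at 15 and 30 min using temperature discrimination to ice". Asymmetry is defined by the same two-dermatome threshold, "as assessed at 15 and 30 min or at any time that sensory levels are checked because of complaints of pain".
- **Neuraxial technique paragraph.** CSE starts with an intrathecal dose only. DPE starts with 20 ml through the catheter, "administered in divided doses of 5 ml every 2 min". In both arms programmed boluses run "every 45 min starting 30 min after the initial spinal or epidural loading dose". Both arms also have "patient-controlled epidural analgesia (PCEA) of 10 ml, a lockout of 10 min and maximum dose of 50 ml per hour", with no separate start time.
- **Secondary outcomes paragraph.** Sensory levels at 15 and 30 minutes are listed, and the list ends with "total anesthetic dose; PCEA use; and overall satisfaction with analgesia".

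**The concern.** Two things look wrong.

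First, the definition is not closed. The component's wording could mean at the 30-minute check or only later than it. Initiation is not tied to time 0. The assessment paragraph also lists a 15-minute check, which the component seems to exclude. Two analysts could classify the same woman differently.

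Second, if the 30-minute reading counts, the same ice test examines different things. In DPE it examines a block produced through the catheter. In CSE it mostly examines the spinal block, because the first programmed epidural bolus is due at the same nominal time as the check. Later sensory checks occur only when a woman complains of pain. A painless one-sided catheter block can therefore become a primary event in DPE but, without early PCEA, not in CSE.

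At stake would be the primary comparison itself: which women count as events, and whether a conclusion for or against DPE rests on a check that tests the catheter in one arm and largely not in the other.

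**Working it through.** **1. Drug given through the catheter before t = 30 min** (neuraxial technique paragraph)

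- DPE: 20 ml load.
- CSE: 0 ml programmed, since boluses start at 30 min.
- PCEA, either arm: if active from time 0, boluses at 0, 10 and 20 min give at most 3 × 10 = 30 ml; if unused, 0 ml.
- Early physician top-up, either arm: possible, but it is already a primary event, so it cannot alter the composite through asymmetry.

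The factual premise holds.

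**2. Does the choice of clock matter?** The DPE load is 20/5 = 4 doses with 3 gaps of 2 min, so at least 6 min pass from first dose to time 0.

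| Check | CSE, from first dose | DPE, from first dose |
|---|---|---|
| t = 15 | about 15 min | at least 15 + 6 = 21 min |
| t = 30 | about 30 min | at least 30 + 6 = 36 min |

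On either clock the first check falls before 30 min and the second at or beyond it, in both arms. No scheduled check is reclassified.

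**3. Which reading is natural?** Set the two sentences side by side. The assessment sentence offers three occasions: 15 min, 30 min and pain-triggered. The component restricts by time. Dropping the 15-minute check and keeping the other two gives both sentences a purpose. The strict reading, later than 30 min only, would leave the component with no scheduled assessment. It is possible but less natural.

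**4. The plan's own figure.** Inputs from the sample size paragraph: 50 per group, 50% v 22.5%, alpha 0.05 (two-sided assumed).

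Power = Φ{[d − 1.96·√(2p̄(1 − p̄)/n)] / √([p₁(1 − p₁) + p₂(1 − p₂)]/n)}

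With d = 0.275, p̄ = 0.3625 and n = 50: (0.275 − 0.1884)/0.0921 = 0.94, so power is 82.6%. The unpooled formula with continuity correction gives 79.0%. The stated 80% lies between these variants.

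**5. How many women could change the conclusion?** Planned rates correspond to about 25 v 11 events. Pearson chi-squared = 100(25·39 − 11·25)²/(36·64·50·50) = 8.51.

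| CSE v DPE events | p, uncorrected | p, continuity-corrected | Risk ratio |
|---|---|---|---|
| 25 v 11 | 0.0035 | 0.0068 | 11/25 = 0.44 |
| 20 v 11 (five fewer in CSE) | 0.052 | 0.084 | 11/20 = 0.55 |
| 25 v 16 (five more in DPE) | 0.067 | 0.104 | 16/25 = 0.64 |

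With the correction, four women suffice (21 v 11, p = 0.054; 25 v 15, p = 0.066). Any five one-sided reclassifications, from any component, would do the same.

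**6. Power under assumed shares** (illustration only). Let q be the share of DPE women, and s of CSE women, who are events only through 30-minute asymmetry. If the planned rates already include both, power stays at 82.6%. If they include neither:

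| q | s | Rates, CSE v DPE | Power |
|---|---|---|---|
| 5% | 0 | 50% v 27.5% | 64.0% |
| 5% | 5% | 55% v 27.5% | 80.7% |
| 0 | 5% | 55% v 22.5% | 92.8% |

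The effect goes either way, and the documents give neither q nor s.

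**The case for a change.** The strongest case for acting is that this is a primary outcome with an open definition, that closing it costs a sentence, and that blinding and an identical test cannot cure a difference in what is tested. With an observed 25 v 15 (uncorrected p = 0.041), one more DPE event gives p = 0.067, so a rule settled only at analysis could decide the result. A sensitivity composite leaving out asymmetry found only at 30 minutes would show whether it did.

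Part of this stands. No sentence settles the point explicitly, and a 30-minute difference in asymmetry should not be read as a difference in catheter function.

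The rest is weaker. Unequal opportunity to detect catheter asymmetry is a defect only if catheter asymmetry is the target, and the stated target is analgesic quality. A lopsided spinal block in CSE is also poor quality, and it also counts. Asymmetry that leads to a top-up or catheter adjustment is an event in both arms whatever the 30-minute rule. The example that removes five CSE events and none from DPE even runs against the suspected direction, which was against DPE. The sensitivity composite would discard genuine spinal asymmetry, might be less comparable with the study behind the planned rates, and would leave the primary result unchanged. Counting CSE women who used PCEA before the check would need time-stamped data, which the documents do not describe.

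**Conclusion.** The concern rests on correct facts but does not call for a change. The wording gap is one that analysts fill sensibly: exclude the 15-minute check, and count the 30-minute and pain-triggered ones. The clock difference of at least 6 minutes changes no scheduled classification. The different blocks at 30 minutes follow from comparing two initiation strategies with the same test, threshold, schedule and blinding; that is a fair design choice, not a measurement error.

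No direction or size of bias can be claimed. The tipping point of four or five women describes any binary outcome with 50 per arm and about 25 v 11 events. The power range of 64.0% to 92.8% comes entirely from assumed 5% shares.

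This conclusion assumes that the primary outcome means what the plan calls it, the quality of analgesia rather than catheter performance, and that the 30-minute check counts. A report that states the rule used and gives asymmetry counts by arm, split into 30-minute and pain-triggered detection, would let readers judge the component. That is reporting detail and leaves the planned primary analysis as it is.
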